3.1 Study Design

This is a phase 3, double-blind, placebo-controlled, randomized study evaluating the effect of evolocumab on coronary atherosclerotic plaques as assessed by OCT at baseline and at week 50 in subjects with an NSTEMI-ACS. The trial duration of 1 year was chosen based on the results of several historical trials. Subjects will be randomized 1:1 into 2 treatment groups no more than 7 days after the signing of the informed consent: evolocumab 420 mg subcutaneously (SC) QM or placebo SC QM. The randomization will be stratified by current statin use (> 4 weeks or ≤ 4 weeks duration) at screening. Investigators will up-titrate statin therapy to the maximally tolerated dose, in accordance with local guidelines, for subjects prior to randomization.

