3.2 Sample Size

The planned total sample size is 150 subjects (75 randomized to evolocumab 420 mg SC QM and 75 randomized to placebo SC QM). This sample size will provide sufficient power (90%) to determine whether there is a treatment effect of evolocumab relative to placebo in the primary endpoint.

The assumptions in the sample size calculation are based on a linear regression meta-analysis of 7 historical trials ([Dai et al, 2017](#); [Hou et al, 2016](#); [Kataoka et al, 2014](#); [Komukai et al, 2014](#); [Nishio et al, 2014](#); [Hattori et al, 2012](#); [Takarada et al, 2009](#)) weighted by sample sizes.

The analysis result indicates that every 1 mg/dL reduction in LDL-C is estimated to be associated with 1.4785 μm increase in FCT in 12-month follow-up. Assuming a 50 mg/dL reduction in LDL-C, the predicted mean increase (95% CI) in FCT from the meta-analysis was 73.92 (50.97, 96.88) μm. For this study, the assumed treatment effect is at least 50.97 μm increase in FCT, which is approximated from the lower bound 95% CI of the expected change in FCT from the regression model, based on a conservative assumption of 50 mg/dL reduction in LDL-C from baseline to week 50.

The SD of FCT measurement at baseline or at the end of various length of follow-up was reported in a wide range (10.6 to 124 μm) based on 15 to 134 subjects per arm in the historical trials. The SD of change in FCT was only reported in 2 of the 7 trials, ranging from 22 to 86 μm. The assumed common SD for this study is 86 μm to be conservative.

Assuming 1 out of 6 subjects will not complete both baseline and week 50 OCT assessments, and therefore be excluded in the primary analysis, the sample size of 150 subjects will provide approximately 125 subjects in the primary analysis to ensure 90% power to test the study hypothesis.

The sample size calculation was performed using a 2-sided t-test with a 0.05 significance level. The sample size calculation was derived using East® software (version 6.4).

4. Covariates and Subgroups

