4.2 Subgroups

Subgroup analysis of the primary endpoint will be conducted for the following subgroups:

Subgroup by stratification factor:

- Current statin use (> 4 weeks or ≤ 4 weeks at the time of screening)

Subgroup by baseline covariates:

- Age (< median, ≥ median; < 65 years of age, ≥ 65 years of age)
- Sex
- Baseline LDL-C (< median, ≥ median)
- Current tobacco use (yes, no)

5. Definitions

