9.5.1 Analyses of Primary Efficacy Endpoint(s)

Primary Analysis:

To assess the primary endpoint of absolute change in minimum FCT from baseline to week 50, an ANCOVA (Analysis of Covariance) model on the FAS will be used, including terms for treatment group, stratification factor (current statin use [> 4 weeks or ≤ 4 weeks] at screening), baseline minimum FCT as covariates. Least square means and corresponding 95% confidence intervals (CI) will be calculated for each treatment group and for the difference between treatment groups. For subjects with missing post-baseline **minimum FCT**, the **post-baseline minimum FCT value** will be imputed

using multiple imputation. The imputation model will include treatment group, stratification factor, baseline LDL-C, baseline minimum FCT, age as covariates. **At least** five imputations will be conducted, and each complete dataset after imputation will be analyzed using the ANCOVA model. SAS PROC MIANALYZE will be used to combine the results from individual ANCOVA models.

Sensitivity Analysis

- 1) Non-parametric analysis (Quade test) will be performed on FAS as sensitivity analysis. The missing data will be imputed using multiple imputation. **The imputation model and the analysis approach of combining results from multiple imputed datasets will be same as the primary analysis.**
- 2) **COVID-19 Impact sensitivity analysis:**
To determine the impact of COVID-19, a sensitivity analyses will be conducted. All the available post-baseline FCT values will be considered in the analysis, irrespective of the analysis visit window (ie, the post-baseline FCT values after week 56 will also be considered for the analysis). The ANCOVA model for COVID-19 Impact analysis will include the covariates of treatment group, stratification factor (current statin use [> 4 weeks or ≤ 4 weeks] at screening), baseline minimum FCT as covariates. The imputation method, model and analysis approach will be same as the primary analysis.

Covariate and Subgroup Analysis

In addition to the primary analysis, covariate adjusted analysis of the primary efficacy endpoint will be performed as supportive analyses using the baseline covariates in [Section 4.1](#), in their original format, one at a time, in the ANCOVA model used in the primary analysis.

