Subgroup analyses on the primary efficacy endpoint will be conducted using the subgroups specified in [Section 4.2](#), in the ANCOVA model used in the primary analysis. Subgroup by treatment interactions will be tested and the p-value of the interaction term will be reported.

For covariate and subgroup analyses, the data-derived stratification factor from the CRF will be used.

Supplementary Analysis:

The following additional analyses will also be performed to evaluate the robustness of the primary analysis result:

- The primary analysis will be repeated using OAS
- The primary analysis will be repeated using CAS

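### Read naturally, the SAP runs the subgroup interaction tests on data imputed with no subgroup-by-treatment term, which weakens real interactions by about the fraction missing

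*SAP*

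**What the plan says.** SAP 9.5 gives the primary analysis as multiple imputation plus ANCOVA on the full analysis set, and SAP 8.3 says that missing primary endpoint values are imputed. SAP 9.5.1 specifies the imputation terms: "The imputation model will include treatment group, stratification factor, baseline LDL-C, baseline minimum FCT, age as covariates". At least five imputed datasets are each analysed by ANCOVA and the results are pooled.

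The subgroup analyses in the same section are fitted within the primary analysis's ANCOVA, and "Subgroup by treatment interactions will be tested and the p-value of the interaction term will be reported". SAP 4.2 lists five factors: statin-use stratum, age (two cut-points), sex, baseline LDL-C (split at the median) and current tobacco use. The one stated departure for the covariate and subgroup analyses is that the stratum comes from CRF data. No observed-value rule and no separate imputation model is given for them.

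**The concern.** The imputation model assumes that the treatment effect is the same in every subgroup. The analysis model then asks whether it differs. Treatment, stratum, LDL-C and age enter the imputation as main effects, with no product term; sex and tobacco use do not enter at all. Imputed subjects therefore dilute any interaction present in the observed subjects.

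The interaction p-values are what a reader would use to judge whether the effect on cap thickness is consistent across patients. If estimates are pulled toward zero and standard errors are inflated, the subgroup display looks more uniform than the observed data warrant. The planned repeats on the OCT and completers sets cover the primary analysis, not the interaction tests, so they would not show the problem.

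**Working it through.** **Inputs.** From SAP 3.2: "the assumed treatment effect is at least 50.97" µm; "The assumed common SD for this study is 86" µm; a calculation "performed using a 2-sided t-test with a 0.05 significance level"; 90% power; 150 subjects; 1 in 6 without both OCT assessments. From SAP 3.1: 1:1 allocation. Subgroup shares, interaction sizes and missingness patterns are not in the documents; they are assumptions, stated where used.

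**1. The plan's own figure.** Normal approximation: n per arm = 2(1.96 + 1.2816)² × 86² / 50.97² = 59.8, so 60. The t-test needs 61 per arm (122 in total). With 125 evaluable, power is 90.8%, and 125 / (1 − 1/6) = 150. The sample size reproduces.

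**2. Attenuation.** Let θ be the true difference in treatment effect between two subgroups and f the missing fraction, spread evenly. Observed subjects contribute θ and imputed subjects contribute 0 on average, so the expected estimate is (1 − f)θ. At f = 1/6, 60 µm becomes 60 × 5/6 = 50 and 100 µm becomes 83.3.

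**3. Standard error.** For a balanced two-by-two layout, with many imputations and ignoring uncertainty in the imputation coefficients:

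- within-imputation variance W = 16σ²/N
- between-imputation variance B = 16fσ²/N
- pooled variance T = W + B = 16(1 + f)σ²/N
- true variance of the estimate = 16(1 − f)σ²/N
- observed values only = 16σ²/[N(1 − f)]

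At f = 1/6, N = 150 and σ = 86, the pooled SE is 86√(16/150 × 7/6) = 30.3, and the true SD is 86√(16/150 × 5/6) = 25.6. Their ratio is √(5/7) = 0.845, so the actual type I error is 2[1 − Φ(1.96/0.845)] = 2.0%.

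| Missing | Factor 1 − f | Actual type I error | Power at 50.97 µm, imputed | Power at 50.97 µm, observed only |
|---|---|---|---|---|
| 10% | 0.90 | 3.0% | 32.8% | 40.6% |
| 1/6 | 0.83 | 2.0% | 25.4% | 38.1% |
| 25% | 0.75 | 1.1% | 16.9% | 34.9% |

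**4. Simulation with the SAP's imputation terms** (N = 150, SD 86, 1/6 missing at random, Rubin pooling).

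- True interaction 50.97 µm, five imputations: the mean estimate is 0.830 of the truth for a 50/50 factor outside the imputation model, 0.843 for a 25/75 factor, 0.832 for age by median and 0.841 for the stratum. Having the factor in the model as a main effect does not remove the shrinkage.
- Same setting: pooled SE about 31.3 against a true SD of about 27.5; null rejection 2.3%, and 2.35% with 50 imputations, so more imputations do not help. Power is about 23% against 36% for observed values.
- Assumed 30% subgroup, 20 imputations, separate runs: 60 µm is estimated as 49–50 and 100 µm as 82–83. The mean SE is about 34 against a true SD of about 28. Null rejection is 1.8–2.8%. Power is 26–28% against about 40% at 60 µm, and 69% against 81–84% at 100 µm.
- With the subgroup and its product with treatment added to the imputation model, the estimates are 59–61 and about 100, and null rejection is 4.7%.

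**5. Uneven missingness.** With patterns averaging about 1/6, the factor was about 0.75 to 0.84. For a factor absent from the imputation model, a prognostic effect (20 µm assumed) with 10% against 23.3% missing by arm gave a spurious interaction of about −2.6 µm.

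**The case against.** The SAP does not say in one sentence that the subgroup tests reuse the primary imputation. For both sensitivity analyses it states that the imputation carries over; for subgroups it does not, and imputing within subgroups would remove the shrinkage. The listed terms might also not be exhaustive. This part of the objection stands as a limit on certainty. But SAP 8.3 imputes the primary endpoint without exempting subgroups, and where the SAP wants observed data it says so, as it does for the exploratory endpoints in 9.5.3. Reuse is the natural reading, and if something else was intended the sentence is still needed.

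The stakes are modest. The tests are supportive and sit outside the multiplicity family. An interaction of 60 µm exceeds the whole assumed treatment effect. For 25 µm, taking SEs of 34 pooled and 28 true under the plan and 34 for observed values, power is roughly 5% against 11–12%, so it would usually be missed either way. That limits the consequence but does not make the reported p-value correct.

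A reader might infer that every interaction is shrunk by a fixed one sixth. The documents do not support that: one sixth is a planning assumption, shrinkage follows what is actually missing, and a zero interaction has nothing to shrink. A reader might also infer a risk of false subgroup claims. With evenly spread missingness the test errs the other way.

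**Conclusion.** The concern holds on the natural reading of SAP 8.3, 9.5 and 9.5.1. A real interaction is attenuated by roughly the realized missing fraction, and its pooled SE overstates its variability. With none, and evenly spread missingness, the estimate is unbiased and the test conservative. The power loss at 60 µm rests on the assumed 30% subgroup, SD 86 and 1/6 missing at random.

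The direction is toward missing heterogeneity. The primary result and the Hochberg-tested secondary endpoints do not change. This is worth correcting before unblinding, but it does not threaten the trial's main conclusion. It also does not follow that the covariate-adjusted analyses need sex, diabetes and tobacco use in their imputation model; no effect of that omission was shown.

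**What to change.** Add one sentence to the covariate and subgroup paragraph of SAP 9.5.1, choosing one of two rules:

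- Subgroup and interaction analyses use observed values without imputation, for example on the OCT analysis set already defined in SAP 6.2.
- For each such analysis, the imputation model also includes the subgroup variable and its product with treatment.

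Either rule brought the estimate and the error rate back close to nominal in the simulations. The first is simpler, but it gives up the age and LDL-C information that the imputation model uses. The second keeps it and needs a few more lines of code per factor. Under both, the subgroup outputs no longer share the primary analysis's imputed datasets, so a table note should say so. The primary analysis is untouched.

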9.5.2 Analyses of Secondary Efficacy Endpoint(s)

The secondary efficacy endpoints will be analyzed using the similar method as used in primary analysis of the primary efficacy endpoint but adjusting for corresponding baseline variable. The Hochberg method for multiplicity adjustment will be used to maintain the overall error rate at 0.05.

9.5.3 Analyses of Exploratory Efficacy Endpoint(s)

The exploratory endpoints will be analyzed using ANCOVA. The model will include change or percent change from baseline for each exploratory endpoint as dependent variable, and terms for treatment group, stratification factor (current statin use [> 4 weeks or ≤ 4 weeks] at screening) and corresponding baseline values as covariates. The p-values displayed will be considered as descriptive. The analysis will be carried out on observed data and missing data will not be imputed.

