
 To evaluate the effects of evolocumab on lipid parameters in subjects with NSTEMI-ACS who are taking maximally tolerated statin therapy To evaluate the effects of evolocumab on features of coronary plaques in subjects with NSTEMI-ACS who are taking maximally tolerated statin therapy using different imaging techniques. 	
 Absolute and percent changes in lipid parameters by visit from baseline. Absolute change in number of microchannels in matched segments of all lesions assessed in an individual subject as determined by OCT from baseline to week 50. Absolute change in macrophage composition in matched segments of all lesions assessed in an individual subject as determined by OCT from baseline to week 50. Absolute changes in lipid content in matched segments of all lesions assessed in an individual subject as determined by IVUS from baseline to week 50.

Page 2 of 2

The primary estimand consists of:

- The target population, which is the adult subjects with NSTEMI-ACS who are taking maximally tolerated statin therapy with or without additional lipid-modifying medication.
- The primary variable, which is the absolute change in minimum FCT in a matched segment of artery as determined by OCT from baseline to week 50.
- The summary measure, which is the mean treatment difference of the primary variable means between evolocumab and placebo.
- The intercurrent events, all randomized subjects who receive at least 1 dose of investigational product regardless of adherence to treatment or commencing commercial proprotein convertase subtilisin/kexin type 9 (PCSK9) inhibitors.

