2.2 Hypotheses and/or Estimations

The primary hypothesis is that low-density lipoprotein cholesterol (LDL-C) lowering with evolocumab 420 mg monthly (QM) will result in a greater increase from baseline in

minimum FCT at week 50 than placebo in subjects taking maximally tolerated statin therapy.

3. Study Overview

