8.3 Handling of Missing and Incomplete Data

Subjects may be missing specific data points for various reasons. In general, data may be missing due to a subject's early withdrawal from study, a missed visit, or non-evaluability of a data point or endpoint at a time. All attempts will be made to capture missing or partial data for this trial prior to the database lock. The frequency of missing data for efficacy endpoints will be assessed through descriptive summaries of the measurements over time. For subjects with missing post-baseline FCT, the missing primary **and secondary** endpoints will be imputed using multiple imputation.

Adverse event and concomitant medication with completely or partial missing start dates will be queried. After the issue is queried, the date is still incomplete with year only or year and month only, the start date will be imputed as described below:

Table 1. Imputation Rules for Incomplete Dates

	Missing	Imputation	Exception
Start date (AE and concomitant medication)	Day	1	Default to Study Day 1 if an event starts the same year and month as Study Day 1
	Day / Month	1-Jan	Default to Study Day 1 if an event started the same year as Day 1

For historical events (eg, date first taken in the prior statin therapy form) that will be used to summarize data derived stratum, the imputation rules are as follows: if the day is missing, default to 1; if both month and day are missing, default to Jan 1. If the imputed date is on or after the randomization date, default to randomization date minus 1.

Missing years will not be imputed under any condition.

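### Minor: week-24 lipids go unused for subjects with no week-50 sample; one repeated-measures model would use them at almost no cost

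*SAP*

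**What the plan says.** The lipid endpoint in SAP 2.1 is exploratory: "Absolute and percent changes in lipid parameters by visit from baseline". Central fasting lipids are drawn on day 1 and at weeks 24 and 50 (Protocol Table 2-1). SAP Appendix A assigns days 2 to 259 to week 24 and every later day to week 50, with no upper limit.

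SAP 9.5.3 fits ANCOVA to change or percent change, with treatment group, statin-use stratum and the corresponding baseline as terms. It calls the p-values descriptive and closes: "The analysis will be carried out on observed data and missing data will not be imputed". SAP 9.1 repeats the no-imputation rule. There is no visit term, no subject effect and no covariance structure. The SAP does not say in words that each visit has its own model. That is inferred from a by-visit endpoint combined with a model that has no visit term.

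The primary hypothesis (SAP 2.2) is that "low-density lipoprotein cholesterol (LDL-C) lowering with evolocumab 420 mg monthly (QM) will result in a greater increase" in minimum FCT than placebo. FCT has its own rule in SAP 8.3, opening "For subjects with missing post-baseline FCT, the missing primary": missing primary and secondary values are multiply imputed.

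**The concern.** With separate by-visit models, a subject who gives a week-24 LDL-C and then has no week-50 sample drops out of the week-50 comparison altogether. That subject's week-24 value is probably the best available predictor of the missing one, and it shows whether the subject was still responding. The plan collects it and then does not use it.

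Two things follow. The week-50 LDL-C difference is somewhat less precise than the data allow. It also depends on the assumption that missing a week-50 sample is unrelated to the lipid response, given treatment, stratum and baseline. A model using both visits needs less: missingness may also depend on the week-24 value. This deserves a line in the SAP because LDL-C lowering is the mechanism named in the primary hypothesis, and readers will look at the week-50 figure.

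**Working it through.** **The plan's own figures.** The documents give no sample size, power, SD or missing rate for lipids. The FCT calculation reproduces. SAP 3.2 states "the assumed treatment effect is at least 50.97" (micrometres), "The assumed common SD for this study is 86" (micrometres) and "The sample size calculation was performed using a 2-sided t-test with a 0.05 significance level". With 150 × 5/6 = 125 evaluable subjects (62 and 63), t-test power is 90.8% against 90% stated. The test needs 61 per arm, and 122/(5/6) rounds up to 147 against 150 planned. The 1/6 used below comes from this calculation. It is the share lacking both OCT assessments, not the share lacking lipids.

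**Precision.** Let m be the share with no week-50 value, missing at random, and ρ the residual week-24/week-50 correlation (assumed). All subjects are taken to have a week-24 value, which favours the repeated-measures model. Relative to complete data:

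- observed-only ANCOVA: V_obs = 1/(1 − m)
- repeated measures: V_rm = 1 + [m/(1 − m)](1 − ρ²)
- SE reduction = 1 − √(V_rm/V_obs)

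| m | ρ | V_obs | V_rm | SE reduction |
|---|---|---|---|---|
| 1/6 | 0.5 | 1.200 | 1 + 0.2 × 0.75 = 1.150 | 2.1% |
| 1/6 | 0.7 | 1.200 | 1 + 0.2 × 0.51 = 1.102 | 4.2% |
| 5% | 0.5 | 1.053 | 1.039 | 0.6% |
| 5% | 0.7 | 1.053 | 1.027 | 1.2% |

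Over ρ from 0.3 to 0.9 the reduction is 0.8% to 7.0% at m = 1/6 and 0.2% to 2.0% at m = 5%. Simulation at m = 1/6 gave 1.9% (ρ = 0.5) and 4.1% (ρ = 0.7).

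In absolute terms, with an assumed residual SD of 30 percentage points, the complete-data SE is 30 × √(2/75) = 4.90 points. At m = 1/6 and ρ = 0.7, observed-only gives 4.90 × 1.095 = 5.37 and repeated measures 4.90 × 1.050 = 5.14. That is about 0.2 points on an effect near 60 points (the approximate percent reduction in Protocol 3.3.1.1).

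**Overstatement against a treatment-policy target.** Assume an on-drug difference of −60 points, no effect off drug, and ρ = 0.7. A share p of the evolocumab arm stops and all of them miss week 50. A share e of these were already off drug at their week-24 sample.

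- treatment-policy value: −60(1 − p)
- observed-only: −60
- repeated measures: −60 + ρ × 60 × p × e

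| p | Treatment-policy | Observed-only | Repeated measures, e = 0 | e = 0.5 | e = 1 |
|---|---|---|---|---|---|
| 5% | −57 | −60 | −60.0 | −59.0 | −57.9 |
| 10% | −54 | −60 | −60.0 | −57.9 | −55.8 |
| 1/6 | −50 | −60 | −60.0 | −56.5 | −53.0 |

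Simulation (75 per arm, SD 30) agreed within 0.2 points. If only half of a 1/6 stopping share leaves, observed-only gives about −54.6. Repeated measures gives about −54.5, −53.0 and −51.3 for e = 0, 0.5 and 1. If every stopper returns, both methods give −50 and neither is biased. In these scenarios repeated measures was not always the more precise: with p = 1/6 and e = 1 the simulated SDs were 5.48 against 5.41.

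**The case against.** The strongest reply is that nothing confirmatory rests on this analysis. Lipid change is exploratory with descriptive p-values. The FCT model and its imputation use no post-baseline LDL-C, and the SAP plans no mediation or slope analysis. That stands, and it is why the point is minor.

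The protocol also limits the problem. Subjects who stop drug are to return for all other measurements (Protocol 7.4.1.1), and Protocol 8.1 presses for them to stay on study. The week-50 lipid window is open-ended, so a sample delayed by COVID-19 still counts. Subjects with target-vessel intervention before week 40 skip the final imaging but keep their other visits (Protocol 9.1.2.1), so lipid missingness may well be below 1/6. All of this stands.

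A reader might infer that separate ANCOVAs cause the week-50 LDL-C effect to be overstated. The documents do not support that. Any overstatement comes from off-drug subjects leaving, and the repeated-measures model removes none of it when they stopped after the week-24 sample. It also presupposes a treatment-policy target, which the documents state only for the FCT estimand; against an on-drug target there is none.

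A reader might also infer that LDL-C and FCT are estimated in materially different populations because FCT is imputed. The contrast is weak. The FCT imputation model (SAP 9.5.1) contains treatment, stratum, baseline LDL-C, baseline FCT and age, with nothing after baseline. With one follow-up, that comes close to an observed-data ANCOVA.

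**Conclusion.** The point holds as a minor improvement. As written, the plan leaves week-24 lipids unused for subjects who miss week 50, given that one model per visit is the sound reading of SAP 2.1 and 9.5.3 together.

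The expected gain is a week-50 SE about 2% to 4% smaller if 1/6 are missing and ρ is 0.5 to 0.7, and 0.2% to 2.0% smaller if 5% are missing (ρ 0.3 to 0.9). There is also a partial reduction in conditional overstatement, confined to subjects already off drug at week 24 who then have no week-50 value. The missing rate for lipids, ρ, the SD, the stopping shares and the zero off-drug effect are assumptions, not figures from the plan. Use of a commercial PCSK9 inhibitor after leaving would change the last of these. The primary FCT test, its power and its imputation are untouched.

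**What to change.** In SAP 9.5.3, for the lipid endpoints only, replace the by-visit ANCOVA with one repeated-measures model on the FAS using all observed week-24 and week-50 values. Terms: treatment, visit, treatment-by-visit, baseline, baseline-by-visit and the stratification factor, with an unstructured covariance. Report the treatment difference and its 95% CI at each visit. Keep ANCOVA for the imaging endpoints, which have a single follow-up.

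Add a table of missing week-50 LDL-C by arm and by whether the subject was on or off drug. SAP 8.3 already calls for missing-data frequencies; the split by drug status shows whether the overstatement that the model cannot remove is a live issue.

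The cost is one SAP paragraph and one table. No new data or subjects are needed, the no-imputation rule can stay, and Protocol 10.3.2.2 leaves exploratory methods to the SAP. The downside is slightly more modelling; with two visits the covariance has three parameters, so fitting should not be a difficulty.
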